| | | 
 • Section 17 SUPPLEMENT 1: Crossover from BSC ALONE (ARM B) to Avelumab plus Best Supportive Care. 
Additional changes:
 
 • For consistency with changes implemented by Protocol Amendment 3, the following sentence was removed from Footnote #3 of the Prior to Protocol Amendment 6: Schedule of Activities for End of Treatment/Withdrawal and Follow-up Periods: “During the post-treatment safety follow-up (beyond 30 days through 90 calendar days after last study administration), AEs (serious or non-serious) that the investigator believes have at least a reasonable possibility of being related to study drug are to be recorded on the case report form (CRF).” • As per Protocol Administrative Change Letter dated 02 Jul 2020, footnote #6 of the Prior to Protocol Amendment 6: Schedule of Activities for Screening and Study Treatment Periods, footnote #5 of the Schedule of Activities for patients who Crossover from Arm B to Avelumab Plus BSC (Supplement 1) and Section 7.1.4 Physical Examinations and Vital Signs were updated to clarify that vital signs should be taken before study drug dosing. • 8.14.2 Non-Serious Adverse Event Reporting Requirements was updated to include an administrative change implemented through a country specific (Japan) Protocol Administrative Change Letter dated 02 July 2020. • As per country specific (Japan) Protocol Administrative Change Letter dated 02 July 2020: Section 12.2 Ethical Conduct |

| Document | Version Date | Summary of Changes |
|-------------|------------------|--|

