8. ADVERSE EVENT REPORTING

8.1. Adverse Events

All observed or volunteered AEs regardless of treatment group or suspected causal relationship to the study treatment(s) will be reported as described in the following sections.

For all AEs, the investigator must pursue and obtain information adequate both to determine the outcome of the AE and to assess whether it meets the criteria for classification as a serious adverse event (SAE) requiring immediate notification to Pfizer or its designated representative. For all AEs, sufficient information should be obtained by the investigator to determine the causality of the AE. The investigator is required to assess causality.

Follow-up by the investigator may be required until the event or its sequelae resolve or stabilize at a level acceptable to the investigator, and Pfizer concurs with that assessment.

As part of ongoing safety reviews conducted by the sponsor, any non-serious adverse event that is determined by the sponsor to be serious will be reported by the sponsor as an SAE. To assist in the determination of case seriousness, further information may be requested from the investigator to provide clarity and understanding of the event in the context of the clinical study.

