8.2. Reporting Period

For SAEs, the active reporting period to Pfizer or its designated representative begins from the time that the patient provides informed consent, which is obtained prior to the patient's participation in the study, ie, prior to undergoing any study-related procedure and/or receiving study treatment, through and including 90 calendar days after the last administration of the study treatment (Arm A) or 90 days after the EOT visit (Arm B). SAEs occurring to a patient after the active reporting period has ended should be reported to the sponsor if the investigator becomes aware of them; at a minimum, all SAEs that the investigator believes have at least a reasonable possibility of being related to study treatment are to be reported to the sponsor.

AEs (serious and non-serious) should be recorded on the CRF from the time the patient has taken at least 1 dose of study treatment (Arm A) or from Cycle 1 Day 1 (Arm B) through and including 90 calendar days after the last administration of study treatment (Arm A) or 90 days after the EOT visit (Arm B).

If a patient begins a new anticancer therapy, the AE reporting period for non-serious AEs ends at the time the new treatment is started. Death must be reported if it occurs during the SAE reporting period after the last dose of study treatment, irrespective of any intervening treatment.

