8.14.2. Non-Serious Adverse Event Reporting Requirements

All AEs will be reported on the AE page(s) of the CRF. It should be noted that the form for collection of SAE information is not the same as the AE CRF. Where the same data are collected, the forms must be completed in a consistent manner. For example, the same AE term should be used on both forms. AEs should be reported using concise medical terminology on the CRFs as well as on the form for collection of SAE information.

For Investigative Sites in Japan Only:

After avelumab is approved for treatment of advanced urothelial carcinoma by the Ministry of Health, Labour and Welfare (MHLW) in Japan, investigators in Japan may be requested by Pfizer to obtain specific additional follow-up information to be provided to Pharmaceuticals and Medical Devices Agency (PMDA) and/or MHLW if a reported treatment-related non-serious AE is found to be unexpected according to the Japanese Prescribing Information. If this occurs, the investigator will be required to pursue and provide the additional information to Pfizer; this information may be more detailed than the information captured on the adverse event case report form. In general, the information will include sufficient detail regarding the description of the adverse event to allow for a complete medical assessment of the case and independent determination of possible causality. Information regarding other possible causes of the adverse event, such as concomitant medications and illnesses, must also be provided.

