8. Current or prior use of immunosuppressive medication within 7 days prior to avelumab treatment (Cycle CR1 Day 1), EXCEPT the following:
 - a. Intranasal, inhaled, topical steroids, or local steroid injections (eg, intra-articular injection);

- b. Systemic corticosteroids at physiologic doses ≤ 10 mg/day of prednisone or equivalent;
 - c. Steroids as premedication for hypersensitivity reactions (eg, CT scan premedication).
9. Diagnosis of prior immunodeficiency or organ transplant requiring immunosuppressive therapy.
10. Vaccination within 4 weeks of the first dose of avelumab treatment and while on trial is prohibited except for administration of inactivate vaccines (for example, inactivated influenza vaccines).
11. Breastfeeding female patients and female patients of childbearing potential who are unwilling or unable to use a highly effective method of contraception as outlined in the protocol [Section 4.3.1](#) for the duration of the study and for at least 30 days after the last dose of investigational product.
12. Other severe acute or chronic medical conditions including but not limited to HIV, HBV, or HCV infection, colitis, inflammatory bowel disease, pneumonitis, and pulmonary fibrosis; psychiatric condition including recent (within the past year) or active suicidal ideation or behavior; or laboratory abnormality that may increase the risk associated with study participation or study treatment administration or may interfere with the interpretation of study results and, in the judgment of the investigator, would make the patient inappropriate for entry into this study.

GENERAL TREATMENT/STUDY PLAN

Patients who crossover from BSC alone to avelumab plus BSC will receive avelumab at 10 mg/kg on Day 1 and Day 15 of each 4-week treatment cycle after all procedures/assessments have been completed as described in the [SOA](#) table.

With the exception of the detailed SOA provided below, all study treatments, concomitant medication restrictions, AE reporting, etc, described for patients randomized to Arm A in [Section 5](#) through [Section 7.1](#) and [Section 8](#) of the study protocol will be followed for patients who crossover from Arm B to avelumab plus BSC.

SCHEDULE OF ACTIVITIES FOR PATIENTS WHO CROSSOVER FROM ARM B TO AVELUMAB PLUS BSC

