| 12. | Urinalysis: Required only at Screening and End of Treatment. To be performed as clinically indicated at other time points. Required tests are listed in Table 6 . |
| 13. | 12-Lead Electrocardiogram (ECG): A single ECG measurement is required at screening. Additional ECGs may be performed as clinically indicated. Clinically significant new findings seen on follow-up ECGs should be recorded as adverse events. |
| 14. | Tumor Assessments: Tumor assessments will be performed according to the local standard of care and when progression is suspected, however the tumor assessment data will no longer be entered into the CRF nor submitted for central imaging review. |
| 15. | Adverse Events: Adverse events (AE) should be documented and recorded at each visit using National Cancer Institute (NCI) Common Terminology Criteria for Adverse Events (CTCAE) version 4.03. For serious adverse events (SAEs), the active reporting period to Pfizer or its designated representative begins from the time that the patient provides informed consent, which is obtained prior to the patient's participation in the study, ie, prior to undergoing any study-related procedure and/or receiving study treatment, through and including 90 calendar days after the last administration of the study treatment. SAEs occurring to a patient after the active reporting period has ended should be reported to the sponsor if the investigator becomes aware of them; at a minimum, all SAEs that the investigator believes have at least a reasonable possibility of being related to study treatment are to be reported to the sponsor. AEs (serious and non-serious) should continue to be recorded on the Case Report Form (CRF) through and including 90 calendar days after the last administration of avelumab. If a patient begins a new anticancer therapy, the AE reporting period for non-serious AEs ends at the time the new treatment is started. Death must be reported if it occurs during the SAE reporting period after the last dose of study treatment, irrespective of any intervening treatment. |

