| 12-lead ECG ¹² | | If clinically indicated | | | |
| Disease Assessments | | | | | |
| Tumor Assessments (including scans) ¹³ | | | X | | |
| Other Clinical Assessments | | | | | |
| Adverse Events ¹⁴ | X | X | X | X | |
| Concomitant Medications/Treatments ¹⁵ | X | X | X | X | |
| New Systemic Anticancer Treatment | X | X | X | X | X |
| Survival Assessment ¹⁶ | | X | X | X | X |

ACTH = adrenocorticotropic hormone; BSC = best supportive care; ECG = electrocardiogram; ECOG = Eastern Cooperative Oncology Group

| Footnotes for SCHEDULE OF ACTIVITIES FOR END OF TREATMENT/WITHDRAWAL AND FOLLOW-UP PERIODS | |
|---|---|
| 1. | Visit Identifiers: Acceptable time windows for performing each assessment are described in the column headers. Per the visit time window, laboratory tests may be performed up to 3 days prior to the scheduled clinic visit so that results will be available for review. |
| 2. | End of Treatment/Withdrawal: Obtain these assessments if not completed in the prior week, except for tumor assessments, which need not be repeated if performed within the prior 6 weeks. |

| | |
|-----|---|
| 3. | 
Short- and Long-Term Follow-up: All patients will be followed for safety every 30 days (± 3 days) through 90 days after the last dose of avelumab. During the post-treatment safety follow-up (beyond 30 days through 90 calendar days after last avelumab administration), AEs (serious or non-serious) that the investigator believes have at least a reasonable possibility of being related to study drug are to be recorded on the case report form (CRF).
 
Beyond the 90 days until the end of the study (long-term follow-up), all patients will be followed every 3 months after the last study clinic visit (± 14 days) for survival, tumor assessment, and new systemic anticancer treatment; additional timepoints to collect survival information may be requested by the Sponsor in preparation for interim and final analyses.
 |
| 4. | 
Physical Examination: Includes an examination of major body systems.
 |
| 5. | 
Vital Signs and Weight: Vital signs to include blood pressure and pulse rate. Blood pressure and pulse rate should be taken with the patient in the seated position after the patient has been sitting quietly for at least 5 minutes.
 |

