| 13. | 
Tumor Assessments: Tumor assessments will be performed according to the local standard of care and when progression is suspected, however the tumor assessment data will no longer be entered into the CRF nor submitted for central imaging review.
 |
| 14. | 
Adverse Events: Adverse events (AE) should be documented and recorded at each visit using National Cancer Institute (NCI) Common Terminology Criteria for Adverse Events (CTCAE) version 4.03. For serious adverse events (SAEs), the active reporting period to Pfizer or its designated representative begins from the time that the patient provides informed consent, which is obtained prior to the patient's participation in the study, ie, prior to undergoing any study-related procedure and/or receiving study treatment, through and including 90 calendar days after the last administration of the study treatment. SAEs occurring to a patient after the active reporting period has ended should be reported to the sponsor if the investigator becomes aware of them; at a minimum, all SAEs that the investigator believes have at least a reasonable possibility of being related to study treatment are to be reported to the sponsor.
 
AEs (serious and non-serious) should continue to be recorded on the Case Report Form (CRF) through and including 90 calendar days after the last administration of avelumab.
 
If a patient begins a new anticancer therapy, the AE reporting period for non-serious AEs ends at the time the new treatment is started. Death must be reported if it occurs during the SAE reporting period after the last dose of study treatment, irrespective of any intervening treatment.
 |

- | |
|---|
| 
15. Concomitant Medications/Treatments: Concomitant medications and treatments should continue to be recorded through and up to 90 days after the last dose of avelumab. If a patient begins a new anti-cancer therapy, reporting of concomitant medications should end at the time the new cancer therapy is started; see Section 5.9 for additional details. All concomitant medications will be recorded in the CRF including supportive care drugs (eg, anti-emetic treatment and prophylaxis), the drugs used to treat adverse events or chronic diseases, and non-drug supportive interventions (eg, transfusions). Concomitant medications should be reviewed at each study visit, and any prohibited treatments (as described in Section 5.9) should be discussed with the patient and appropriately managed.
 |

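### Crossover follow-up footnotes 3 and 14 give different CRF rules for adverse events on days 31 to 90, and no text says which governs

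*Protocol*

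**What the plan says.** The conflict lies within one table, the crossover End of Treatment/Withdrawal and Follow-up schedule in Protocol Supplement 1.

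- **Footnote 3**, attached to the Follow-up column header, covers the period beyond day 30 through day 90 after the "last avelumab administration), AEs (serious or non-serious) that the investigator believes have at least a reasonable possibility of being related to study drug"; these are the events it says are to go on the CRF.
- **Footnote 14**, attached to the Adverse Events row, says "AEs (serious and non-serious) should continue to be recorded on the Case Report Form (CRF) through and including 90 calendar days" after the last avelumab dose. Its one limit is that recording of non-serious events stops when a new anticancer therapy starts.

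The other relevant passages agree with footnote 14:

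- Footnote 15 of the crossover treatment schedule: events "should continue to be recorded on the Case Report Form (CRF) through and including 90 calendar days after the last administration of avelumab".
- Section 8.2, for Arm A: recording runs "through and including 90 calendar days after the last administration of study treatment (Arm A").
- Section 8.1: "All observed or volunteered AEs regardless of treatment group or suspected causal relationship to the study treatment(s) will be reported".
- Section 8.14.2: "All AEs will be reported on the AE page(s) of the CRF".

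The general plan in Supplement 1 carries the Arm A rules over to crossover patients with a carve-out: "With the exception of the detailed SOA provided below, all study treatments, concomitant medication restrictions, AE reporting, etc" are to be followed as for Arm A.

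**The concern.** Two footnotes to the same cells tell a site different things. Under footnote 14, an event on day 45 that the investigator judges unrelated goes on the CRF. Under footnote 3, as a site would naturally read it, the requirement narrows after day 30 and that event can be left off.

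What is at stake is the completeness of late safety data in crossover patients. Footnote 3 covers serious as well as non-serious events, so a serious event judged unrelated could be in the sponsor's safety database but missing from the CRF. Section 8.14.2 expects the two to be consistent where they collect the same data.

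**Working it through.** This is a comparison of texts; no alpha, power or event count enters.

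**Step 1. The CRF rule for days 31 to 90 after the last avelumab dose**

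| Source | Causality condition |
|---|---|
| Supplement 1 follow-up schedule, footnote 3 | Possibly related events |
| Supplement 1 follow-up schedule, footnote 14 | None |
| Supplement 1 treatment schedule, footnote 15 | None |
| Section 8.2 (Arm A) | None |
| Sections 8.1 and 8.14.2 | None |
| Amendment 6 schedule, footnote 12 | None |

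**Step 2. Does footnote 3 restrict?** It does not contain the word *only*. But it draws a line at day 30 and names a subset defined by causality. If every event is recorded through day 90 anyway, neither the line nor the subset does any work. The sentence has a function only if it narrows the requirement.

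**Step 3. Does any text set precedence?**

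- The opening of Supplement 1 applies the main protocol to matters the supplement does not address. This matter is addressed, twice.
- The general plan imports Section 8 but exempts the crossover schedule of activities. Both footnotes sit in that schedule, so the exemption does not choose between them.
- The introduction to the crossover schedule moves all patients to the Amendment 6 schedule once Amendment 6 is implemented and the final OS update is done. That ends the conflict from then on but does not settle it before.

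**Step 4. Comparison with the other follow-up schedules.** Footnote 3 of the main follow-up schedule and footnote 3 of the Amendment 6 schedule have no such sentence. The amendment log gives the background for the main schedule: "For consistency with changes implemented by Protocol Amendment 3, the following sentence was removed from Footnote #3". The log does not mention the copy in Supplement 1. The finding rests on the two current footnotes, not on the log.

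**Step 5. Size of the disputed window**

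- Days: 90 − 30 = 60, and 60 / 90 = 67% of the post-treatment recording period. This is an upper bound; for non-serious events it shortens when a new anticancer therapy starts.
- Visits: the Adverse Events row is marked at End of Treatment, day 30, day 60 and day 90. By nominal day, 2 of the 4 (day 60 and day 90) collect events from the disputed window.

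These figures measure time and visits, not events lost. The documents do not give the number of crossover patients.

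**Step 6. Where the data would be used.** SAP Section 5.2.7 ends the on-treatment period at the latest 30 days after the last dose. Later safety data are listed and flagged but not summarized. The irAE case definition in SAP Appendix 1 (step 2) accepts onset through 90 days after the last dose and works from AE records in the CRF, so an event left off the CRF cannot enter it. The SAP is based on Amendment 4, whereas the crossover came with Amendment 5, so the SAP plans no crossover analysis.

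**The case against.** The best case against is that this is leftover wording, not a contradiction. Footnote 3 never tells a site to omit anything, and a site that records everything under footnote 14 complies with both. The Adverse Events row itself points to footnote 14. The introduction to the crossover schedule sends readers to the Assessments section for detail, and Section 7.1.2 there has events during the study recorded on the adverse events CRF page without a causality filter. Under Section 8.9, an event of unknown causality is handled as related for reporting purposes, so only events positively judged unrelated could be missed. No planned analysis changes, and nothing shows that any event was in fact left off.

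Much of this stands. The all-events reading is the better supported one, the affected set is small, and the consequence for an irAE review is conditional on someone doing one. What does not follow is that the text is harmless. Footnote 3 heads the follow-up columns and so also governs the day 60 and day 90 cells. Its day 30 boundary and causality subset serve no purpose unless they restrict, and no passage states that footnote 14 or Section 8 overrides it. Weight of agreement among other passages is not a precedence rule that a site can apply.

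**Conclusion.** The concern holds and is minor. While the crossover schedule is in force, two of its footnotes give different CRF rules for days 31 to 90, and the protocol does not say which applies. The exposure is at most 60 days per crossover patient, for events judged unrelated; for non-serious events it ends earlier if a new anticancer therapy starts. Serious events still reach the sponsor through day 90 regardless of causality. Overall survival, the randomized comparison and the 30-day treatment-emergent summaries are not affected. The adverse event listings, and any 90-day irAE review of crossover patients, could be incomplete.

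The conclusion assumes that a sentence with a day 30 boundary and a causality criterion is meant to restrict. How many events were omitted, if any, cannot be estimated from the documents.

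**What to change.** Delete the related-events sentence from footnote 3 of the Supplement 1 follow-up schedule, so that footnote 14 governs and all follow-up schedules agree. This costs one sentence and requires no data beyond what footnote 14 already asks for.

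In addition, send sites a short memo asking whether any day 31 to 90 events were left off the CRF under footnote 3 and, if so, to enter them. That involves some retrospective checking at sites with crossover patients in follow-up. The text correction does not depend on it.

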1. VERSION HISTORY

This Statistical Analysis Plan (SAP) for study B9991001 is based on the protocol amendment 4 dated 28-Mar-2019.

Table 1. Summary of Major Changes in SAP Amendments

Version	Version Date	Summary of Changes
1	23-Dec-2015	Not applicable (N/A)
2	02-Apr-2019	
Section 2.1 “Study Objectives”, Section 3.3 “Exploratory Endpoints”, Section 6.3 “Other Endpoints” updated to remove irRECIST objectives and endpoints as per protocol amendment 4.
 
Section 2.2 “Study Design” was updated to reflect changes made in protocol amendment 3.
 
Section 3.2.2 “Efficacy endpoints” – corrected the definition of disease control to include best overall response (BOR) of non-CR/non-PD to take into account patients without measurable disease at baseline; clarified the criterion for SD must have been met at least 6 weeks after the date of randomization as per protocol.
 
Section 3.4.1 “Study drug, study treatment and baseline definitions” – added definition of end date of study treatment; added definition of baseline for immunogenicity analyses; removed definition of baseline for ECG assessments as no summaries will be provided (ECGs are only collected post-treatment if clinically indicated).
 
Section 3.4.2 “Baseline characteristics” – updated the stratification factor from “Best response to first-line chemotherapy per BICR assessment” to “Best response to first-line chemotherapy” to reflect changes made in protocol amendment 3.
 
Section 3.5.1 “Adverse events” – updated the definition of treatment-emergent adverse events; clarified that start of new anti-cancer drug therapy is used in the definition of on-treatment period.
 
Section 4.2 “Safety Analysis Set” – clarified that patients randomized to Arm B that incorrectly received avelumab will be classified in Arm A for the purpose of safety analyses.
 
Section 4.3.1 “Per-protocol analysis set” – updated the definition of PP analysis set to align with the key inclusion/exclusion criteria.
 
Section 5.1.2 “Decision rules” – added description of primary analysis of OS; updated Table 6 to reflect correct simulated operational characteristics of the study design and added a footnote to clarify that the actual interim and final analyses will occur at the same calendar time for both patient populations.
 
Section 5.2.5 “Definition of start of new anti-cancer drug therapy”, Section 5.2.6 “Definition of start of new anti-cancer therapy”, Section 5.2.10 “Adequate baseline tumor assessment” and Section 5.2.11 “Adequate post-baseline tumor assessment” were added to provide the details associated with derivations used to define the on-treatment period and to implement censoring in efficacy analyses.
 
Section 5.2.7 “Definition of on-treatment period” – clarified that start of new anti-cancer drug therapy is used in the definition of on-treatment period.
 
Section 5.3.2.4 “Exposure” – clarified that in imputation derivations the cutoff date is used as last dosing date in the analyses of patients that have study drug ongoing at the time of the cutoff date.
 
Section 5.3.3.1 “Date of last contact” – added withdrawal of consent date in the


	
derivation of date of last contact.
 
Section 5.3.3.2 “Death date” imputations – deleted the last step in the imputation “if the day is missing from the date of last contact it will be imputed to 1st day of the month and year of last contact only if derived from the ‘Survival Follow-up’ eCRF page” since not needed.
 
Section 5.3.3.4 “Date of start of new anti-cancer therapy” was added to provide details of imputation rules for incomplete dates for start date of new anti-cancer therapy (drug therapy, radiation, surgery).
 
Section 5.3.3.5 “PRO data” was added to provide details of imputation rules for missing PRO data.
 
Section 6.1.1 “Overall Survival” – added that RCIs will be calculated for the analyses of OS; provided more details and hierarchy associated with the derivation of reasons for censoring; provided more details on the analysis of time of follow-up for OS.
 
Section 6.2.2 “Efficacy Endpoints” – clarified that the efficacy endpoints will be summarized for both co-primary populations; provided more details on analysis of PFS and Time of Follow-Up for PFS; provided more details and hierarchy associated with the derivation of reasons for censoring for PFS; added details on the assessment of concordance for PFS between investigator and BICR assessments.
 
Section 6.2.2.2 “Sensitivity analyses for overall survival” – deleted the sensitivity analysis based on CRF-derived randomization stratification factors since the data collected in the eCRF does not enable unequivocal derivation of the stratification factors; provided additional details for checking the proportional hazard assumption and added further details regarding implementation of restricted mean survival (RMST) methodology.
 
Section 6.2.2.3 “Objective response and tumor shrinkage” – added definition of BOR of non-CR/non-PD for patients without measurable disease at baseline; added analysis to assess association of study treatment and objective response; added summary for BOR discrepancy between BICR and Investigator; provided further granularity for reasons for not evaluable BOR.
 
Section 6.2.2.4 “Disease Control” – added non-CR/non-PD in the definition for disease control to take into consideration the patients without measurable disease at baseline. Removed the original planned analysis for DCR at 24 weeks since more adequately summarized based on Kaplan-Meier rates for PFS.
 
Section 6.2.2.5 “Duration of response” – added details regarding censoring for duration of response since “no adequate baseline assessment” which is used in censoring for PFS analyses is not applicable to analyses of duration of response for patients with objective response.
 
Section 6.2.3 “Pharmacokinetic endpoints” – provided additional details for the analysis of C_{trough}, C_{max} and plasma concentrations.
 
Section 6.2.5 “Biomarker endpoints” – exploratory biomarker endpoints were updated to be consistent with protocol amendment 3.
 
Section 6.2.6 “Endpoints for Immunogenicity Data of Avelumab” – added details for the analysis of ADA and nAb.
 
Section 6.2.7 “PRO endpoints” and subsections – added details for the analysis of PRO data.
 
Section 6.4 “Subset Analyses” – Added clarification that the subset analyses will be performed for both the co-primary populations; removed the subset analysis based on “response to first-line chemotherapy as assessed by BICR” to reflect the updates in protocol amendment 3; added subset analysis based on baseline liver lesions and baseline lung lesions; updated the p-value for the interaction test to

--	--

	
be based on Wald's test; removed forest plots for median DR by subgroup.
 
Section 6.5.1 "Baseline summaries" – Added clarification that the baseline summaries will be tabulated for both co-primary populations; updated geographic region classifications.
 
Section 6.5.1.3 "Disease characteristics" – removed some analysis to align with data collection as per updates made to eCRF.
 
Section 6.5.1.4 "Prior anti-cancer therapies" – clarified that the prior anti-cancer therapy information will be included in the listing of anti-cancer therapies with a flag to identify prior therapies.
 
Section 6.5.1.5 "Exposure to first-line anti-cancer chemotherapy regimen" – removed summary for number of cycles, dose intensity and relative dose intensity since prior to randomization.
 
Section 6.5.2.1 "Patient disposition" – removed summaries based on CRF-derived randomization stratification factors since the data collected in the eCRF does not enable unequivocal derivation of the stratification factors; removed the summary of reason for randomization not equal to treatment assignment since data collected in eCRF does not enable such analysis.
 
Section 6.5.3 "Study Treatment Compliance and Exposure" – added additional details for summary of exposure to avelumab; removed by-cycle summaries; added details for derivation and summary of dose delays.
 
Section 6.5.3.5 "Infusion interruptions" was added.
 
Section 6.5.5 "Subsequent anti-cancer therapies" – added summary of follow-up anti-cancer drug therapies for patients with PD-L1-positive tumors.
 
Section 6.6.1 "Adverse events" and subsections – updated definition of treatment-emergent adverse event. Given the nature of immune-related AEs (irAEs) and infusion related reactions (IRRs), removed the summaries of treatment-related irAEs and treatment-related IRRs; removed the requirement that all summaries by SOC and PT will be replicated by PT only. Added summaries of AEs leading to dose reduction, AEs leading to interruption of study treatment and AEs leading to both dose reduction and interruption of study treatment.
 
Section 6.6.1.2 "Adverse events leading to dose reduction" and Section 6.6.1.3 "Adverse events leading to interruption of study treatment" were added.
 
Section 6.6.2 "Death" – deleted references to primary reason for death since not collected in the eCRF.
 
Section 6.6.4 "Other significant adverse events" – given the nature of the study and BSC as comparator arm, nominal p-values for risk difference for Tier-1 events will not be calculated.
 
Section 6.6.5 "Laboratory data" and subsections – Changed the formula for corrected calcium to be expressed in SI units; clarified that the denominator to calculate percentages for each laboratory parameter is the number of patients evaluable for the particular summary; added summary for patients with newly occurring or worsening laboratory abnormalities; updated lab parameters that will be summarized in shift tables.
 
Section 6.6.7 "Electrocardiogram" – removed the analyses of ECGs that are not applicable to this study as ECGs are only collected when clinically indicated.
 
Section for "Physical Examination" was removed as data not collected in the eCRF.
 
Section 7 "INTERIM ANALYSES" – added details for the calculation of the boundary for final efficacy analysis.
 
Section 8 "REFERENCES" – references updated.
 
Section 9 "APPENDICES" – added appendices with the irAE and IRR derivation

--	---

		rules; deleted the tabulation of cycle derivations since included with more details in the exposure section. Minor editorial and consistency changes throughout the document.
--	--	--

